# **Study Summary**

Study Outline	Atrial fibrillation (AF) is the most prevalent type of arrhythmia within an adult population and is characterised by disorganised, chaotic, electrical activity and thus, ineffective atrial contraction causing irregular ventricular contraction. AF can be categorised into three different groups: paroxysmal, persistent and permanent. The prevalence of AF increases with age and is associated with a range of risk factors including: hypertension, obesity and alcohol consumption. There is a plethora of both cardiac and non-cardiac causes of AF and the cause is not always clear for each patient. Furthermore, causes of AF can also present as the by-product of AF, this increases the difficulty in determining the individual patient's cause of onset. A diagnosis of AF can be incidental as not all patients are symptomatic. If AF goes undetected, this puts the patient at an increased risk of blood clot formation and stroke.
	Patients suspected of having AF are routinely referred for a transthoracic echocardiogram (TTE). It is common for AF patients to have a dilated left atrium (LA). This can be visually confirmed, and the LA area and volume can be measured during a TTE. LA strain measurements are not routinely measured during TTEs but may be able to detect subtle changes in longitudinal strain patterns of the myocardium. By comparing the strain patterns in patients with normal sinus rhythm (control) to those with AF, a scale can be created to suggest and predict whether a patient is likely to develop AF in the future based on these subtle changes before any changes in LA size occur. Furthermore, this can then be further developed to determine whether there are any significant differences in strain patterns between the three AF groups.
Lay Summary	Atrial fibrillation (AF) is the most common type of abnormal heart rhythm. This occurs as the chambers of the heart pump irregularly, often resulting in a fast heart rate and symptoms of irregular pounding and fluttering. There are many risk factors predisposing to AF, however, the cause cannot always be easily determined. Additionally, not all AF patients experience symptoms and consequently, this abnormal rhythm may go undetected and may be discovered accidentally. This is detrimental to patients, as untreated AF patients are at an increased risk of stroke.
	Patients that are suspected of having AF are referred for an ultrasound scan of the heart (echocardiogram). It is expected to see structural changes to the heart's chambers. However, structural and electrical changes of the heart may be the cause of AF but may also be a result of AF, resulting in a chicken and egg situation. It may be possible that a different type of measurement can be used during an echocardiogram to detect subtle changes in heart muscle patterns. This measurement may then serve to be an early predictor of AF. This would be determined by comparing the patterns in patients with a normal, regular rhythm to those with AF.
	Potential candidates are initially screened based on their echocardiogram referral. If deemed suitable for this study, the study

	process is explained to the patient and written informed consent is invited and received. The echocardiogram will be performed as normal with a focus on the area and volume measurements taken of one of the top chambers of the heart. An additional measurement will be taken to observe any subtle changes in the arrangement of heart cells within this same heart chamber. These measurements can be compared to each other to establish any relationship as well as compared to patients with and without AF.
Objectives	To determine whether there is a significant difference in atrial strain values between patients that are in normal sinus rhythm (NSR, control group) to patients that are known to have atrial fibrillation (disease group). A disease-control group of controlled hypertensive patients in NSR will also be utilised as hypertension is a known risk factor for atrial fibrillation.
	Providing that there is a significant difference in the values between NSR and AF patients, a further comparison will be conducted on patients in different type of AF: paroxysmal AF, persistent AF and permanent AF to determine if there is a deterioration in atrial strain values within AF patients.
	Left atrial area and volume size will also be measured in all patients and this can then be compared to atrial strain values.
Sample Size	234
Duration	1 year – project end date of March 2024

# **Statement of Compliance**

The study as detailed within this protocol (Version 6, 17/05/2023) or any subsequent amendments will be conducted in accordance with the International Conference on Harmonization guidelines for Good Clinical Practice (ICH E6), the UK Policy Framework for Health and Social Care Research (2017), the World Medical Association Declaration of Helsinki (1996) and the current applicable regulatory requirements and any subsequent amendments of the appropriate regulations.

# Abbreviations:

AF	=	atrial fibrillation
AFI	=	automated function imaging
ANOVA	=	analysis of variance
BSE	=	British Society of Echocardiography
CI	=	Chief Investigator
EF	=	ejection fraction
GDPR	=	general data protection regulation
GLS	=	global longitudinal strain
HRA	=	Health Research Authority
ICF	=	Informed Consent Form
LA	=	left atrium/atria
LV	=	left ventricle
NHS	=	National Health Service
NSR	=	normal sinus rhythm
PACS	=	picture archiving system
PAF	=	paroxysmal atrial fibrillation
PALS	=	peak atrial longitudinal strain
PI	=	Principal Investigator
PIS	=	Participant Information Sheet
REC	=	Research Ethics Committee
R&D	=	Research & Development
STE	=	speckle tracking echocardiography
TTE	=	transthoracic echocardiogram

# **1. Introduction**

Atrial fibrillation (AF) is the most prevalent type of arrhythmia within an adult population and is characterised by disorganised, chaotic, electrical activity and thus ineffective atrial contraction causing irregular ventricular contraction (Wyndham, 2000). AF can be categorised into three different groups: paroxysmal, persistent, and permanent. The prevalence of AF increases with age and is associated with, but not limited to, a range of risk factors including hypertension, obesity, and alcohol consumption (Staerk, *et al.*, 2017). There is a plethora of both cardiac and non-cardiac causes of AF and the cause is not always clear for each patient. Furthermore, causes of AF can also present as the by-product of AF, this increases the difficulty in determining the individual patient's cause of onset. A diagnosis of AF can be incidental as not all patients are symptomatic. If AF goes undetected, this puts the patient at an increased risk of blood clot formation and stroke (Markides and Schilling, 2003).

Patients suspected of having AF are routinely referred for a transthoracic echocardiogram (TTE). It is common for AF patients to have a dilated left atrium (LA) and this can be visually confirmed in addition to the LA area and volume measurements (Van De Vegte, et al., 2021). However, as LA measurements are limited to area and volume size, LA strain measurements may be taken but these are not routinely performed during standard TTEs. LA strain is measured using a type of speckle-tracking echocardiography (STE) technique which focuses on the subtle longitudinal changes within the myocardium to analyse myocardial deformation (Gan, et al., 2018). Strain imaging of the LA produces three functional strain values (contractile, conduit and reservoir) which correspond to different stages of the cardiac cycle (Jarasunas, et al., 2018). As patients in AF lack normal atrial contraction and have a loss of atrial kick, it is expected that the contractile strain, associated with LA contraction, is not present. However, the conduit and reservoir functions can still be compared across all three study groups to create a scale to suggest and predict whether a patient is likely to develop AF in the future; prior to any changes in LA size. Furthermore, this can then be further compared to determine whether there are any significant differences in strain patterns between the different groups of AF.

The correlation between AF and a dilated LA are widely recognised, however, LA enlargement may be both a cause and consequence of AF. Dilation of the LA has been largely suggested to be due to atrial remodelling as a result of a change in atrial function and structure – as seen in the case of AF. However, there are other factors which affect atrial function and structure which ultimately result in atrial remodelling. This includes pathologies such as mitral valve disease (mitral stenosis, regurgitation, or a mixed disease), structural cardiac disease (such as heart failure, cardiomyopathies, and congenital disease) and hypertension (Van De Vegte, *et al.*, 2021). As hypertension can also cause atrial remodelling and is a risk factor for AF, patients that are in normal sinus rhythm (NSR) that have controlled hypertension are included in this study as a disease-control group. It is expected that the atrial strain values of these patients will fall between those of the control group (NSR) and of those in the disease group (chronic AF).

Existing available literature (see document Literature Review Table) suggests that there is a significant difference in the strain values between patients in NSR to those in AF. However, limited studies have included hypertensive patients or investigated

the differences in strain values between AF patients. Furthermore, previous studies have been limited by method technique. This is because many studies have either used external STE software to create atrial strain values or have adopted global longitudinal strain (GLS) methods to track the LA. This is a significant limiting factor as GLS methods are intended to assess longitudinal function of the left ventricle.

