# 1.1 Background

From the current literature available (*see document Literature Review Table*), it has been suggested that there is a correlation between AF and LA strain values. Existing literature suggests that patients in AF have a reduced LA strain value compared to patients in NSR. However, there are limited studies which also include controlled hypertensive patients despite collecting data regarding blood pressure. Furthermore, the majority of literature reviewed appears to focus on patients that have other comorbidities, and it could be argued that these can affect the parameters measured and analysed. This includes studies involving patients with valvular pathologies such as aortic stenosis and aortic valve replacements as well as studies involving patients with potential structural heart deformations such as those seen with heart failure or following a myocardial infarction. These factors may alter strain patterns and LA size as a result. By listing these factors as exclusion criteria, this study should minimise any external and uncontrollable factors which may affect LA strain value and LA size.

Furthermore, some studies do not have a standardised zero-reference point as some studies used the P wave for NSR and the R wave for AF patients which may cause a discrepancy in results. In this study, it has been agreed that the zero-reference point will be the R wave to create R-R cycles. This is because the P wave is not present in AF and thus cannot be used as a definitive reference point within the AF group. Both groups will have R waves present and therefore, the reference-point can be standardised across all three groups. Additionally, many of the studies reviewed appear to focus on only one LA strain and phase within the cardiac cycle. However, some do include all three. This study will include all three strain values as well as peak atrial longitudinal strain (PALS) values. However, statistical analysis may not be doable for the contractile phase as this is not present in patients with AF. The biggest pitfall that is common to most, if not all, studies reviewed is that the methods used to calculate LA strain were originally designed to measure global longitudinal strain (GLS) of the left ventricle (LV). This study utilises the automated function imaging (AFI) LA atrial strain tool provided by GE Healthcare which is specific to the LA as opposed to GLS methods to track the LV.

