#### 2.2.5 Power Calculation

The study aims to investigate significant differences in atrial strain values between subjects with atrial fibrillation (AF), hypertension (no AF), and healthy volunteers. To

achieve statistical power for this study, a large enough sample size must be obtained. This will be achieved via the use of power calculations utilising G\*Power 3.1 Statistical support has been provided and a sample size calculation was based on data found within the literature and involved detecting the smaller difference of left atrium contractile % between subjects with atrial fibrillation and healthy volunteers. The following criteria will be utilised: alpha level of 0.05, beta level of 15% and statistical power of 85%. Hence using this minimum value to determine our sample size (expected difference of 4.0, power = 0.85 and SD  $\pm$  7.5) and one-way ANOVA at three levels, a minimum sample size of at least 78 subjects in each group will be required for this study, total of 234 participants required. See Appendix Figures 1 & 2 for power calculation plots.

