#### 2.2.6 Statistical Analysis Plan

Continuous data normality will be assessed utilising the Shapiro-Wilk test. Nonparametric data will be analysed via Mann-Whitney U tests and Kruskal-Wallis oneway ANOVA tests. If data shows a normal distribution, to compare the LA strain values between the control (NSR) and disease (AF) groups an independent T-test can be performed; this will establish whether there is an initial statistically significant difference between the two. Following this, to compare the mean strain values for each phase between the three groups, a one-way ANOVA must be performed. A one-way ANOVA can also be performed to determine any significant differences between the strain values between AF groups. These data analysis methods will also be repeated to analyse LA area and volume. To assess whether LA area and volume size correlate with LA strain, a Pearson correlation coefficient must also be performed. Furthermore, to determine whether LA strain may be used as an early predictor of AF, linear regression models must be adapted. For categorical data, such as gender, chisquared tests will be performed to determine any significant difference between groups. All statistical tests will be performed using the Prism GraphPad software.

It is expected that there will be a significant difference in strain values between NSR and AF participants. It is also expected that an increase in LA area and volume size will correlate with a decrease in LA strain values.

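### Under the usual split of an R-R strain curve, conduit strain in AF duplicates reservoir strain, so the three-group conduit comparison sets unlike quantities side by side

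*Combined protocol and SAP*

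**What the plan says.** Section 1.1 sets a common zero for all groups: "it has been agreed that the zero-reference point will be the R wave to create R-R cycles". Section 1 names three functional values (reservoir, conduit and contractile) and says of AF that "it is expected that the contractile strain, associated with LA contraction, is not present". Section 1.1 draws one consequence, that "statistical analysis may not be doable for the contractile phase as this is not present in patients with AF".

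Neither section carries the consequence over to conduit strain. Section 1 says that "the conduit and reservoir functions can still be compared across all three study groups to create a scale", and that scale is meant to predict later AF. Section 2.2.6 makes the test compulsory: "to compare the mean strain values for each phase between the three groups, a one-way ANOVA must be performed". Section 1.1 adds a fourth value: "This study will include all three strain values as well as peak atrial longitudinal strain (PALS) values".

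Section 2.2.5 bases the sample size on "detecting the smaller difference of left atrium contractile % between subjects with atrial fibrillation and healthy volunteers", with a difference of 4.0 and an SD of 7.5. No section says where conduit strain starts or ends, how it is read when there is no atrial contraction, or whether the curve is taken to return to zero.

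**The concern.** The plan treats the missing contractile phase as a problem for the contractile analysis only. On a curve that runs from one R wave to the next, the phases share the same fall from the peak. If one phase disappears, its neighbour may take over its part. The label conduit would then mean one thing in sinus rhythm and another in AF.

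Three things are at stake:

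- **Interpretation.** A small or null conduit difference could be read as preserved conduit function in AF. Section 1 also expects hypertensive values to lie between the other two groups, and for conduit that ordering could fail through the definition alone.
- **The predictive scale.** It is to use conduit and reservoir together. If the two are one number in AF, agreement between them is not independent support.
- **Secondary analyses.** Correlations with atrial area and volume would mix the two meanings if conduit is pooled across rhythms. The AF-subtype comparison would do so too if some paroxysmal patients are scanned in sinus rhythm.

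Sections 2.2.6 and 2.3 name no primary strain measure, so conduit has the same standing as reservoir.

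**Working it through.** **1. The plan's own figure.** Group means of 0, 2 and 4 with SD 7.5 give f = √[((−2)² + 0² + 2²)/3] / 7.5 = 1.633/7.5 = 0.2177, the effect size in the Appendix Figure 1 output. With N = 234, λ = 0.2177324² × 234 = 11.093, critical F = 3.035 and power = 0.851. The 234 reproduces. It rests on contractile strain.

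**2. Inputs.** From the documents: R-wave zero, R-R cycles, three phases, no contractile phase in AF. Assumed, because the documents do not say: conduit runs from the peak to the onset of atrial contraction, or to the next R wave if there is none; the curve returns to about zero.

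**3. Algebra, in absolute values.** Let P be the peak and A the strain at the onset of atrial contraction.

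- Sinus rhythm: reservoir = P; contractile = A − 0 = A; conduit = P − A. So conduit = reservoir − contractile.
- AF: reservoir = P; there is no contractile part; conduit = P − 0 = P. So conduit = reservoir.

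Write L for the reservoir loss (sinus rhythm minus AF) and C for the mean contractile strain in sinus rhythm. Then

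conduit difference = (P_NSR − C) − P_AF = L − C.

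If the curve ends at a residual e instead of zero, and e is the same in both groups, then C = A − e and AF conduit = P_AF − e. The difference is (P_NSR − A) − (P_AF − e) = L − (A − e) = L − C again. Only unequal drift between groups changes it.

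**4. Size.** The documents give neither L nor C. The table shows L − C in strain points over assumed ranges. The value C = 4 is the section 2.2.5 difference if AF contractile strain is exactly 0.

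| L | C = 4 | C = 8 | C = 12 | C = 16 |
|---|---|---|---|---|
| 2 | −2 | −6 | −10 | −14 |
| 4 | 0 | −4 | −8 | −12 |
| 6 | 2 | −2 | −6 | −10 |
| 8 | 4 | 0 | −4 | −8 |
| 12 | 8 | 4 | 0 | −4 |
| 16 | 12 | 8 | 4 | 0 |
| 20 | 16 | 12 | 8 | 4 |

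Positive entries mean that AF conduit is lower, as expected, but the difference is short of L by C. Zero means no difference, and negative means that AF conduit is higher although its reservoir strain is lower.

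**5. PALS.** With the zero at the R wave, the peak of the curve is the reservoir value under the same definitions. In AF, reservoir, conduit and PALS would then be a single measurement.

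**The case against.** The strongest reply is that the identity is not in the documents. They do not define conduit or say what the GE tool reports as conduit in AF. If the tool ends conduit elsewhere in AF, the shift has a different size. This stands: the identity must be labelled an assumption, and the missing definition is itself part of what needs repair.

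A reader might infer that the conduit test loses power, or that its result is biased. That does not follow. Conduit strain does not estimate reservoir loss. If L = C, mean conduit is equal in the two groups and a non-significant test is the right answer for conduit as measured. The fault lies in what the comparison means.

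A reader might also infer that the AF conduit result will be hidden or reversed. The documents do not support this, because they give neither L nor C. The 4.0 in section 2.2.5 is a difference between groups, and with SD 7.5 it is a doubtful mean for a magnitude that cannot be negative. Where L is well above C, the direction is right.

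Listing PALS separately is redundancy and biases nothing. It matters only if agreement with reservoir is counted as extra evidence.

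Finally, the R-wave zero does standardise something: it keeps reservoir strain comparable across groups. It does not standardise where conduit ends.

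**Conclusion.** The point holds as a correction that should be made, short of one on which the study depends. Under the stated definition and a return to about zero, the compulsory conduit comparison between sinus rhythm and AF measures L − C. It always falls short of the reservoir loss by the whole sinus-rhythm contractile strain; it is null at L = C and reversed only below that. How far this matters in practice cannot be settled from the documents.

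Reservoir comparisons keep one meaning in all groups. Normal rhythm versus controlled hypertension is unaffected on every phase, since both groups are in sinus rhythm. Atrial area and volume comparisons between groups are also untouched.

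**What to change.** - **Section 2.2.6:** define conduit strain by rhythm at the scan, including its end point in AF. Use reservoir strain as the strain measure compared between sinus rhythm and AF and in the predictive scale. Restrict conduit and contractile tests, including those in the AF-subtype analysis and any pooled correlations, to participants in sinus rhythm at the scan. Report AF conduit descriptively, as redundant with reservoir.
- **Section 1:** remove conduit from the statement on comparison across all three groups.
- **Section 1.1:** state that PALS and reservoir are treated as one measure under the R-wave reference and are not counted as independent evidence.
- **Section 2.2.5:** note that the sample size rests on an AF-versus-healthy contractile difference that section 1.1 says may not be analysable, and restate its basis for reservoir strain.

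The cost is one fewer three-group comparison and rewording in four sections. The sample-size restatement needs a reservoir difference and SD that the documents do not give, so whether 234 would change cannot be said here. No new scans or data items are needed: section 2.2.2 already lists rhythm and strain among the data collected.

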The key outcomes from this study will be whether there is a significant difference in atrial strain values between NSR patients, controlled hypertensive patients and patients with either persistent or permanent AF. These electrical changes should correlate with structural changes within the LA as the LA becomes more dilated in AF patients. Furthermore, subtle differences in LA strain values may be observed between patients with paroxysmal atrial fibrillation (PAF), persistent and permanent AF to suggest a decline in atrial strain patterns with a worsening and prolongation of AF.

This will have a significant impact to the general population as AF is the most common arrhythmia. Left atrial enlargement and dilation can occur, either as a cause or complication of AF. However, the detection of this structural change and cardiac remodelling by measuring LA area and volume is often only detected when the patient has been in AF for a prolonged period of time. The utilisation of speckle-tracking echocardiography (STE) and atrial strain measurements may be able to detect subtle changes in LA strain pattern which may occur before any significant cardiac remodelling and LA dilation, and thus serve as an early predictor of AF. This will allow for closer monitoring and the correct administration of anticoagulants. Furthermore, the results from this study will also be generalisable and transferrable and may suggest that LA strain measurements should be more routinely performed during TTEs.

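### The plan asks whether strain predicts AF but has no analysis of how well strain separates individuals; its only planning effect, for contractile strain, corresponds to an AUC of about 0.65

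*Combined protocol and SAP*

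**What the plan says.** The Study Summary and the Introduction look ahead to a scale built from strain, in the Introduction from the conduit and reservoir phases, "to create a scale to suggest and predict whether a patient is likely to develop AF in the future". Section 1.2 asks whether strain, with LA area and volume, can serve as an early predictor of AF. Section 1.1 adds that the results may suggest that "LA strain measurements should be more routinely performed during TTEs".

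Section 2.2.6 lists a t-test or Mann-Whitney test of NSR against AF. It then says that "to compare the mean strain values for each phase between the three groups, a one-way ANOVA must be performed", with Kruskal-Wallis as the non-parametric alternative. It adds Pearson correlations of strain with LA area and volume, and chi-squared tests for categorical data. Prediction is assigned to linear regression, with no outcome variable, covariates or performance measure named. The key outcome in section 2.3 is a significant difference in strain between groups.

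The sample size in section 2.2.5 is based on "detecting the smaller difference of left atrium contractile % between subjects with atrial fibrillation and healthy volunteers". Its inputs are "expected difference of 4.0, power = 0.85 and SD" 7.5, and it concludes that "a minimum sample size of at least 78 subjects in each group will be required for this study, total of 234 participants required".

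**The concern.** A scale that tells one patient from another is a claim about individuals. Tests of means, correlations and an unspecified linear regression do not measure that. AF status is binary. If it is coded 0/1 and regressed on strain in two groups, the test of the slope is the equal-variance t-test again, so the regression in its simplest form adds nothing about classification.

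The study could therefore meet its own criterion, a significant difference, and go on to discuss a scale and wider use of strain without having examined how far the groups overlap. The data to examine this will already have been collected. The gap is separate from the absence of follow-up: even the separation of people who have AF today from those who do not is left unanalysed.

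**Working it through.** **Inputs.** Difference 4.0, SD 7.5, three groups, at least 78 per group, alpha 0.05 and power 0.85 (section 2.2.5). Effect size f = 0.2177324 and total 234 (Appendix, Figure 1 output).

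**1. Reproduce the plan's figure.** Evenly spaced means 0, 2, 4 have a standard deviation of √(8/3) = 1.633, so f = 1.633/7.5 = 0.2177. With N = 234, λ = 234 × 0.2177324² = 11.093. The critical F on 2 and 231 df is 3.0349 and power is 0.8509. This matches the output. (The figure captions give an effect size of 0.25, which would need only 180 in total. The captions should be reconciled with the output, but the steps below do not depend on them.)

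**2. Chance of a significant NSR-AF result at the planned effect.** A two-group t-test with 78 per group, difference 4.0 and SD 7.5 has power of about 0.91.

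**3. Discrimination at the planned effect.** Assume normal data with a common SD.
- d = 4.0/7.5 = 0.533.
- AUC = Φ(d/√2) = Φ(0.377) = 0.647.
- Sensitivity and specificity at the midpoint cut-off = Φ(d/2) = Φ(0.267) = 60.5% each.

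**4. Discrimination at the smallest significant difference.** The critical difference is t(0.975; 154 df) × 7.5 × √(2/78) = 1.975 × 7.5 × 0.1601 = 2.37. Then d = 2.37/7.5 = 0.316 and AUC = Φ(0.316/√2) = 0.588.

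**5. AF against controlled hypertension.** With the evenly spaced means of step 1, this difference is 2.0, so d = 0.267 and AUC = 0.575.

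**6. Range for phases with no stated effect.** The document gives no difference or SD for reservoir or conduit strain. Keeping SD 7.5 as an assumption:

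| Assumed difference | AUC |
|---|---|
| 2.4 | 0.59 |
| 4 | 0.65 |
| 6 | 0.71 |
| 8 | 0.77 |
| 10 | 0.83 |
| 15 | 0.92 |

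An AUC of 0.80 needs a difference of 0.8416 × √2 × 7.5 = 8.9.

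**7. Precision available.** The Hanley-McNeil standard error at A = 0.647 with 78 against 78 uses q₁ = A/(2−A) = 0.478 and q₂ = 2A²/(1+A) = 0.508. SE = √{[A(1−A) + 77(q₁−A²) + 77(q₂−A²)]/78²} = 0.044, giving a 95% interval of about 0.56 to 0.73. The planned sample can therefore estimate an AUC to within about ±0.09 (1.96 × 0.044).

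**The case against.** Several points can be made for the plan, and most of them stand.

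- **The planning effect is for another phase.** The 4.0 and 7.5 belong to contractile strain, which section 1.1 expects to be absent in AF and perhaps not analysable. The scale would use conduit and reservoir strain. Section 2.2.5 also treats 4.0 as the smaller difference and as a minimum for sizing. This stands. A reader might infer that the scale will misclassify 4 in 10 people (100 − 60.5 = 39.5%). The document does not support that: the figure is for contractile strain, existing AF against NSR, equal group sizes, a midpoint cut-off and equal variances.
- **Regression is planned.** A reader might infer that the scale rests on mean differences alone. Section 2.2.6 does assign prediction to a regression. The fault is that the regression is unspecified, unsuited to a binary outcome and without a discrimination measure.
- **The scale is not a formal aim.** It appears in the Study Summary and Introduction but not in sections 2.1 or 2.3, and the statement on routine use is hedged. This stands and limits the weight of the point. Sections 1.2 and 2.2.6 still pose the prediction question.
- **No predictive value is promised.** The 78 is a minimum per group, and nowhere is an absolute probability planned. This stands. It is still worth ruling one out, because the share with AF is set by recruitment to groups.
- **Same-day classification is not the intended use.** Rhythm is recorded anyway (section 2.2.2), and section 2.4 plans no follow-up. This also stands. A reader might infer that a high AUC here would support a claim about future AF. It would not, at any value.

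**Conclusion.** The concern holds in a limited form. Section 2.2.6 answers a prediction question with linear regression on what is a binary outcome, and nothing in the plan measures how well strain separates individuals. Significance does not stand in for this. At the only effect the document states, the NSR-AF test would be significant about 91% of the time while the underlying AUC is about 0.65, and a barely significant observed difference corresponds to about 0.59.

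These AUCs assume normality and a common SD, take 78 per group, describe existing AF against NSR, and come from contractile strain. They show that significance and usefulness can part company; they do not forecast how a reservoir or conduit scale would perform, which could be better or worse. The group comparison itself is unaffected. The plan should be changed before analysis, but the study is not undermined.

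**What to change.** In section 2.2.6:

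1. Replace the linear regression with logistic regression of AF status on reservoir and conduit strain, fitted for chronic AF against NSR and for chronic AF against controlled hypertension. State any covariates.
2. Report the AUC with a 95% confidence interval for strain and, alongside it, for LA volume. For any cut-off, give sensitivity and specificity corrected for optimism by bootstrap.
3. State that these results describe discrimination of existing AF only, and that no absolute likelihood or predictive value is taken from a sample whose AF share is set by group recruitment.

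In the Study Summary, section 1 and section 1.1, word the scale and routine-use statements so that they are neither based on p < 0.05 alone nor presented as evidence on future AF. They should not be made to depend on a cross-sectional AUC threshold either, since passing it would say nothing about who later develops AF.

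The cost is a change of SAP wording and slightly more analysis, with no new patients or measurements. If the software named in section 2.2.6 does not offer the bootstrap step, a second package must be named. The downside is a possibly less favourable headline.
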